8.5.2 Other specific reactions

Treatment of these adverse reactions is at the discretion of the investigators; the following suggestions are provided:

- After the first occurrence of flu-like symptomatology including fever, subjects can be treated with standard therapeutic dose of acetaminophen (preferable), or a NSAID if acetaminophen is contraindicated.
- Ensure adequate hydration of trial subjects on the day of vaccination, e.g., by asking trial subjects to drink water before each site visit and during the ~2 h after each IMP administration per trial site standard.

If subjects experience enhanced respiratory disease or progression of flu-like symptomatology (e.g., no improvement of the symptoms after 3 d, or symptom kinetics that are inconsistent with a relationship to RNA vaccination), additional diagnostic measures should be considered, and the trial Medical Monitor should be informed.

8.6 Pharmacokinetics

Pharmacokinetic parameters are not evaluated in this trial.

8.7 Genetics

[figure not shown]
A blood sample (blood and/or isolated peripheral blood mononuclear cells) will be taken to evaluate the association between the human leukocyte antigen (HLA) and the immune response elicited by BNT165b1 CCI

Clinical Trial Protocol Trial number: BNT165-01 Page 53 of 82 Version: 4.0 Date: 13 FEB 2023

CCI			

8.8 Immune responses

Immune responses will be assessed at the times listed in the SoA (Section 1.3). Instructions on the sample collection, handling, and shipping will be provided in a Laboratory Manual.

Humoral immune response assessments will include:

Clinical Trial Protocol Trial number: BNT165-01 Page 54 of 82 Version: 4.0 Date: 13 FEB 2023

Additional immunological assessments may be conducted with residual samples to further characterize the vaccine-induced immune response and/or support vaccine-specific assay development.

Biosamples for research will be retained for use for up to 15 years (or shorter if required by local regulations) after the end of the trial. The tube with the biosample will be labeled with a number (optionally also with a bar code) and will not include information that could be used to identify the subject. Results of the analyses will be linked to the clinical information collected during the trial using this specific number. The analysis will only be carried out on the basis of the label data and biosamples. Research biosamples and all data generated using the biosamples, will be handled in accordance with applicable laws and regulations; this includes requirements applicable for data protection and a potential withdrawal of consent.

8.9 Blood collection

The total blood volume drawn over any 8-week period in any cohort will always be less than 550 mL. Additional blood samples may be taken, e.g., for safety assessments after AEs or SAEs.

The total volume of blood drawn for subjects will be up to ~1,594 mL each.

8.10 Collection of demographic and other baseline characteristics

At screening, the following data will be recorded for all trial subjects:

- Age
- Sex
- Ethnic group
- Race
- Body weight and height, derived body mass index

Medical history information will be recorded for at the times given in the SoA (Section 1.3).

8.11 Unscheduled visits

In order to conduct evaluations or assessments required to protect the wellbeing of the trial subjects, the investigator may conduct unscheduled visits in addition to those listed in the SoA.

Page 55 of 82 Version: 4.0 Date: 13 FEB 2023

8.12 Early termination visit(s)

If, for any reason, subjects are permanently discontinued from the trial before completing all scheduled visits, subjects will complete an Early Termination Visit. If possible, all assessments planned for the actual week or day of that visit as listed in the SoA (Section 1.3) should be performed.

9 STATISTICAL CONSIDERATIONS

9.1 Statistical hypotheses

No formal statistical hypotheses will be tested.

9.2 Sample size determination

The sample size for each cohort is mainly driven by a telescoping dose escalation study in a limited number of subjects designed for early detection of potential safety and reactogenicity events. The sample size of 16 subjects receiving the vaccine per cohort allow the detection of the most frequent AEs with high probability. For 20 subjects, the probability of detecting at least 1 AE is 88% if the underlying AE rate is 10% and if the AE rate is 15%, then the probability of detecting at least 1 AE is 96%.

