4.1.1 Planned number of trial subjects

A total of 60 subjects are expected to enroll in the cohorts evaluating BNT165b1, such that there are 20 trial subjects for each of the cohorts as planned. Per cohort, trial subjects will

Clinical Trial Protocol Trial number: BNT165-01 Page 27 of 82 Version: 4.0 Date: 13 FEB 2023

be randomized 4:1, using an online randomization tool to receive either vaccine or placebo (i.e., of 20 subjects, 16 subjects and 4 subjects will receive the vaccine or placebo, respectively).

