4.2 Scientific rationale for the trial design

Because of the exploratory nature of the trial, no formal sample size calculation was performed. Based on prior experience with such type of trial, the sponsor considers the chosen sample size of 20 subjects per cohort to allow (i) detection of the most frequent systemic and local adverse events (AEs), thereby allowing dose escalation decisions, and (ii) immunogenicity analyses of sufficient scope to support dose selection decisions, to meet the trial objectives, while minimizing the number of trial subjects exposed to the investigational trial treatment BNT165b1. For further justification of the chosen sample size, see Section 9.2.

Since BNT165b1 will be evaluated for the first time, this trial uses a staggered, sequential approach for subject dosing. Dosing will proceed with an initial 2-subject sentinel group for each DL cohort, pause/stopping rules will be followed, and there will be ongoing monitoring by a trial IRC that may pause, permanently discontinue administration of trial treatment, or even permanently terminate the trial at any time.

This trial includes safety monitoring after each dose, including vital signs at ~1 h after each dose, investigator assessment of local reactions up to 1 h after each dose, site visits at ~24 h after Doses 1 and 2, wellbeing phone calls at 5 h, and ~48 h after Doses 1 and 2, wellbeing phone calls at 5 h, ~24 h, and ~48 h after Dose 3, daily investigator review of subject's e-diary data for 7 d after each dose. Also, wellbeing phone calls will be conducted at 14 (+1) d after each IMP dose and local injection site reactions will be solicited starting after 7 d and through 14 d post-IMP administration.

The monitoring focuses on the 48 h after each dose based on experience with the closely related BNT162b2 vaccine in clinical trials, where the most frequent adverse reactions in subjects 16 years of age and older who received two doses were injection site pain (>80%), fatigue (>60%), headache (>50%), myalgia (>40%), chills (>30%), arthralgia (>20%), pyrexia and injection site swelling (>10%), and these adverse reactions were usually mild or moderate in intensity and resolved within a few days after vaccination.

This trial uses safety evaluations and vaccine-induced immune responses to assess if there is a dose-response. For further details refer to Section 8.8.

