- Data from Control group/ placebo recipients will not support the pausing rules.

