8 STATISTICAL ANALYSES

8.1 General considerations

In general, all summaries will be displayed by individual vaccine DL and combined placebo. A total group, combining all subjects on placebo and active vaccine, will be presented in addition for accounting (subject disposition), demographics and other baseline characteristics and protocol deviations as applicable unless otherwise specified.

No formal statistical comparisons between vaccine DL of BNT165b1 and placebo will be performed. Missing data, other than that described for partial or missing dates for AEs/concomitant medications/vaccinations (as described below) will not be imputed.

Continuous variables will be summarized using the following descriptive statistics: number of subjects with non-missing data (n), mean, SD, median, minimum (min) and maximum (max).

Categorical variables will be summarized by absolute and relative frequencies (n and %) of subjects in each category and the number of subjects with missing data ('missing' category will be presented if there is one or more missing value).

For event-driven occurrence data (e.g., adverse event, concomitant medication, etc.) percentages will be based on the number of subjects in the analysis set (N). For reported visit data (e.g., lab etc.) percentages will be based on the number of subjects with non-missing values (n).

The rates of binary endpoints such as safety variables (systemic and local reactions) will be provided.

Page 13 of 36 Version: 3.0 Date: 08 MAY 2024

All data collected during the trial will be listed based on safety set unless otherwise specified. The trial day will be presented as appropriate. Listings will be sorted by dose level, site number, subject number, and date of assessment or date of onset (if applicable).

All trial data will be presented at the visit as assigned in the Case Report Form (CRF). No windowing of data for the purposes of assigning to a visit will occur. Unscheduled assessments will not be included in summaries/analysis but will be included in the listings.

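### The 88% and 96% chances of seeing at least one AE are computed for 20 subjects per cohort, but only 16 receive vaccine; for 16 the figures are 81% and 93%

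*Protocol*

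**What the plan says.** Protocol 9.2 (Sample size determination) makes its claim about vaccinees: "The sample size of 16 subjects receiving the vaccine per cohort allow the detection of the most frequent AEs with high probability". The next sentence supplies the numbers, but for a different group: "For 20 subjects, the probability of detecting at least 1 AE is 88% if the underlying AE rate is 10"%. Its second figure, on the same basis, is 96% for a rate of 15%. SAP 6 carries the same two sentences.

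Protocol 4.1.1 fixes the split within a cohort: "of 20 subjects, 16 subjects and 4 subjects will receive the vaccine or placebo, respectively".

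Protocol 4.2 says that "no formal sample size calculation was performed" and refers the reader to Section 9.2 for further justification. It also ties detection to the full cohort, describing "the chosen sample size of 20 subjects per cohort to allow (i) detection of the most frequent systemic and local adverse events", and links that detection to the dose escalation decisions.

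On how the data will be used, SAP 8.1 says that "all summaries will be displayed by individual vaccine DL and combined placebo", and the notes to the cohort pausing rules in Protocol 7.1.1 say: "Data from Control group/ placebo recipients will not support the pausing rules".

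**The concern.** The two sentences in Protocol 9.2 do not fit together. The first is about 16 people who receive BNT165b1; the second gives probabilities for 20 people, four of whom receive saline. A saline recipient can have an adverse event, but not one caused by the vaccine, and so adds nothing to the chance of finding a vaccine reaction. No dose level has 20 vaccine recipients.

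Because no formal sample size calculation was done, these two probabilities are the only numerical support for the cohort size in either document. In a first-in-human trial they are what an ethics committee or regulator would read as the design's ability to reveal harm at each dose level. If they are too high, readers will place more weight on an absence of events than 16 exposures justify, and the same figures may be carried into the clinical trial report.

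**Working it through.** **Inputs**

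- Rates considered: p = 10% and p = 15% (Protocol 9.2, SAP 6).
- Number used in the text: n = 20 (same sections).
- Vaccine recipients per cohort: n = 16, with 4 on placebo (Protocol 4.1.1).

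**Formula.** If each subject independently has the event with probability p, the chance of at least one event among n subjects is 1 − (1 − p)^n, and the chance of seeing none is (1 − p)^n.

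**Step 1: reproduce the stated figures (n = 20)**

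- p = 10%: 1 − 0.90^20 = 1 − 0.1216 = 0.8784, i.e. 88%.
- p = 15%: 1 − 0.85^20 = 1 − 0.0388 = 0.9612, i.e. 96%.

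Both match. Pooling across cohorts does not: 48 vaccinees give 99.4% and 99.96%. The stated figures therefore come from n = 20.

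**Step 2: repeat for the vaccinated group (n = 16)**

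- p = 10%: 1 − 0.90^16 = 1 − 0.1853 = 0.8147.
- p = 15%: 1 − 0.85^16 = 1 − 0.0743 = 0.9257.

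| True rate | At least one event, n = 20 | At least one event, n = 16 | No event, n = 20 | No event, n = 16 |
|---|---|---|---|---|
| 10% | 87.8% | 81.5% | 12.2% | 18.5% |
| 15% | 96.1% | 92.6% | 3.9% | 7.4% |

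The overstatement is 0.8784 − 0.8147 = 0.0637 (6.4 percentage points) at 10%, and 0.96124 − 0.92575 = 0.03549 (3.5 points) at 15%. As a share of the correct miss probability, the shortfall is 1 − 0.1216/0.1853 = 34% and 1 − 0.0388/0.0743 = 48%.

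**Step 3: rate at which 16 vaccinees deliver the stated probabilities**

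- 88%: p = 1 − 0.12^(1/16) = 12.4%.
- 96%: p = 1 − 0.04^(1/16) = 18.2%.

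**Step 4: does the broader claim survive?** For 16 vaccinees the probability is 97.2% at a 20% rate and 99.7% at a 30% rate. Protocol 4.2 lists most reactions to the related vaccine at above 20%; only pyrexia and injection site swelling are listed at above 10%. The qualitative statement about the most frequent events therefore stands.

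**Step 5: later doses.** Protocol 7.4 does not replace discontinued subjects, and the calculation allows for no dropout. The documents give no dropout rate. As an assumption for illustration, 15 remaining vaccinees would give 79.4% and 91.3%, and 14 would give 77.1% and 89.7%. So 81.5% and 92.6% are upper values for Doses 2 and 3.

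**The case against.** The strongest reply is that nothing has been miscalculated. The sentence names 20 subjects, and its numbers are right for 20. It speaks of an adverse event, not a vaccine-caused one, and Protocol 10.4.1 defines adverse events without regard to causality, so saline recipients can have them. The estimands in Protocol 3 are worded per dose-level cohort, a cohort is 20 randomized subjects, and the committee's escalation review covers all 20. Finally, no hypothesis is tested, and no pausing rule, escalation decision or analysis uses 88% or 96%.

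Parts of this stand. The arithmetic for 20 is correct and the number is disclosed. The estimand wording is loose enough to include placebo recipients, so the case for 16 should not rest on it. The consequences are limited.

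The defence of 20 as the right number does not stand. If the placebo rate is q, the chance of at least one event in the cohort at a 10% vaccine rate is 1 − 0.90^16 × (1 − q)^4. That is 81.5% when q = 0 and reaches 87.8% only when q = 10%, that is, when the event is equally common on saline. An event of that kind is background, not the reactogenicity the paragraph sets out to detect. The preceding sentence is explicitly about vaccinees, safety is tabulated by vaccine dose level with placebo pooled across cohorts, and placebo data are excluded from the pausing rules.

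**Conclusion.** The concern holds. Protocol 9.2 and SAP 6 support a statement about 16 vaccinees with probabilities for 20 subjects. For the 16 who receive vaccine at each dose level, the figures are 81% and 93% (81.5% and 92.6%), not 88% and 96%. The result assumes independent subjects, full dosing of all 16, and an interest in events arising among vaccine recipients; it needs no figure from outside the documents.

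The text is wrong as written, in the optimistic direction, on the design's only stated operating characteristic. The practical impact is modest: the differences are 6.4 and 3.5 percentage points, the trial is descriptive, and the claim about the most frequent reactions remains true with 16.

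**What to change.** In Protocol 9.2 and SAP 6, replace the sentence on 20 subjects with wording such as: *With 16 vaccine recipients per cohort, an AE with a true rate of 10% would be seen at least once with probability 81%, and one with a true rate of 15% with probability 93%.*

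In Protocol 4.2, refer to the 16 vaccine recipients where the text speaks of detecting AEs. That sentence gives no probability, so this change is for consistency. It would also help to state that the figures apply to Dose 1 with all 16 dosed, since discontinued subjects are not replaced.

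If the protocol is not reopened, correct SAP 6 and use the corrected figures in the clinical trial report. The cost is wording only: enrolment, allocation, analyses and conduct are unchanged, and the stated probabilities become slightly less favourable.

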9.3 Analysis sets

The following analyses sets are defined:

Analysis set	Description	
Screened Set	All subjects who provided informed consent	
Safety Set	All subjects who received at least one dose of the IMP	

Abbreviation: IMP = investigational medicinal product

9.4 Statistical analyses

Statistical analyses will be performed by BioNTech or a designated CRO. All statistical analyses will be carried out using SAS®, Version 9.4 or higher, and/or other statistical software as required.

The statistical analysis plan (SAP) will be finalized before the first database lock, and it will include a more technical and detailed description of the statistical analyses described in this section. Any deviations from the planned analyses described in the final SAP will be identified and justified in the SAP and reported in the clinical trial report.

This section gives a summary of the planned statistical analyses of the most important endpoints including primary endpoints.

9.4.1 General considerations

In general, data will be summarized by DL.

Clinical Trial Protocol Trial number: BNT165-01 Page 56 of 82 Version: 4.0 Date: 13 FEB 2023

Continuous variables will be summarized by group using the following descriptive statistics: number of subjects (n), mean, standard deviation, geometric mean, geometric coefficient of variation, median, minimum and maximum.

Categorical variables will be summarized by group presenting absolute and relative frequencies (n and %) of subjects in each category.

Baseline is defined as last available value prior to first BNT165 administration.

9.4.2 Safety endpoints

The safety endpoints are defined in Section 3. All safety analyses will be based on the Safety Set, overall, by vaccine DL or placebo.

All AEs will be coded using the most recent version of MedDRA® coding system to get a system organ class and PT for each AE.

Reactogenicity - Subject-reported via the e-diary

Solicited local and systemic reactions (from the subject e-diary) will be summarized. In general, solicited reactions will be analyzed for each immunization, i.e.:

Up to 7 d after each IMP injection

For each injection, the number and percentage of subjects reporting at least one local reaction or systemic reaction (i.e., solicited data collected using subject e-diaries) will be summarized for each of the following types:

- Any local reactions or systemic reactions
- Grade 1, 2, or ≥3 local reactions or systemic reactions

Moreover, the number and percentage of subjects reporting at least one local reaction will be summarized by worst grade.

Unsolicited AEs

The number and percentage of subjects reporting at least one AE (defined in Section 10.4.1) will be summarized by PT nested within system organ class for each of the following AE types:

- Any AE
- Related AE
- · Grade of AE
- Related Grade ≥3 AE
- Any solicited reactogenicity event that continues longer than 7 d post-IMP administration or is an SAE
- Any SAE
- Related SAE

Moreover, the number and percentage of subjects with any AE will be summarized by worst grade by PT nested within system organ class.

Page 57 of 82 Version: 4.0 Date: 13 FEB 2023

Additional safety analyses may be described in the SAP.

9.4.3 Exploratory endpoints

The exploratory endpoints are defined in Section 3. Exploratory analyses will be described in the SAP, if relevant to the clinical trial report (CTR).

9.4.4 Other safety analyses

Details of the other safety analyses will be described in the SAP.

9.4.5 Other analyses

Other analyses, if relevant to the CTR will be described in the SAP.

9.5 Interim analyses

An interim report with safety and immunogenicity data may be prepared when subjects in any cohort have completed 28 d of follow-up after second or third injection to inform further clinical development. Also, interim reports at other time frames may be prepared.

10 SUPPORTING DOCUMENTATION AND OPERATIONAL CONSIDERATIONS

10.1 Regulatory, ethical, and trial oversight considerations

This trial will be conducted in accordance with this protocol, the ethical principles that have their origin in the Declaration of Helsinki, ICH GCP guidelines, and applicable laws and regulations.

10.1.1 Regulatory and ethical considerations

This trial will be conducted in accordance with the protocol and with the following:

- Consensus ethical principles derived from international guidelines including the Declaration of Helsinki and Council for International Organizations of Medical Sciences (CIOMS) International Ethical Guidelines
- · Applicable ICH GCP Guidelines
- Applicable laws and regulations

The protocol, protocol amendments, ICF, IB, and other relevant documents, will be submitted to the relevant regulatory authorities as required by applicable regulations. If required, approval for conducting the trial will be obtained from regulatory authorities in accordance with relevant regulatory requirements.

The protocol, protocol amendments, ICF, IB, and other relevant documents (e.g., advertisements) will be submitted to an IRB/IEC and reviewed and approved by the IRB/IEC before the trial is initiated.

Clinical Trial Protocol Trial number: BNT165-01 Page 58 of 82 Version: 4.0 Date: 13 FEB 2023

Any amendments to the protocol will be submitted for IRB/IEC approval and (if required) competent authority approval before implementation of changes made to the trial design, except for changes necessary to eliminate an immediate hazard to trial subjects.

The principal investigator or delegate will be responsible for the following:

- Providing written summaries of the status of the trial to the IRB/IEC annually or more frequently in accordance with the requirements, policies, and procedures established by the IRB/IEC.
- Notifying the IRB/IEC of SAEs or other significant safety findings as required by IRB/IEC procedures.
- Providing oversight of the conduct of the trial at the site and adherence to requirements of 21 CFR, ICH guidelines, the IRB/IEC, European regulation 536/2014 (if applicable), and all other applicable local regulations.
- Informing the sponsor immediately of about any urgent safety measures taken by the investigator to protect the trial subjects against any immediate hazard, and of any serious breaches of this protocol or of ICH GCP that the investigator becomes aware of.

The principal investigator, any investigator(s), the sponsor, or personnel at other establishments, must cooperate with any inspection of the documents, facilities, records, and other resources deemed appropriate by the inspecting authorities to be related to the trial and that may be located at the trial site, at the sponsor, or at other establishments.

The sponsor must be notified as soon as possible about any upcoming regulatory authority inspection.

10.1.2 Financial disclosure

All investigators will provide the sponsor with sufficient, accurate financial information as requested to allow the sponsor to submit complete and accurate financial certification or disclosure statements to the appropriate regulatory authorities. Investigators are responsible for providing information on financial interests during the course of the trial and for 1 year after completion of the trial.

